10 PROCEDURES FOR PATIENT ENTRY ON STUDY

This study will be open for accrual at the James Comprehensive Cancer Center at OSU. As part of the screening process, interested patients who meet initial eligibility requirements will be contacted by research staff and the specific requirements, risks/inconveniences, and other details of the research will be explained. Patients will have an opportunity to have all their questions and concerns about the research study addressed. The goal of this session is maximum understanding of the program requirements and its impact on their life. This process is designed to meet ethical obligations to the participant and improve retention by fostering a positive relationship between the participant and the research staff. The person obtaining informed consent will tell the patient that 1) participation is voluntary, 2) participation or non- participation will not affect their usual care and management, and 3) patient confidentiality will be maintained in the event that the results of the

study are published. Patients will be provided with a consent form to review, and all questions answered. After signed informed consent has been obtained, a study identification number will be assigned to the patient for use on all data collection forms and samples.

11 POTENTIAL RISKS AND MANAGEMENT

Because we will be obtaining information about a participant's medical history, lifestyle behaviors, and measuring biomarkers that will become part of the electronic health record, there is a chance that we will uncover or discover sensitive information regarding a person's health status. Although unlikely, this information could cause emotional distress, increase personal expense for treatment, or, if obtained by insurance companies or employers, could be used as justification to raise insurance rates or affect employability. To ensure privacy/confidentiality, information that is received from patients will be kept confidential to the extent allowed by law. Patient data will be entered into the electronic health record and hard copies will be kept in a secure filing cabinet on site for the duration of the study. We will assign all patients a code number to be used on forms, sample collection containers and other research materials. Subject codes will be employed for database management and when statistical analyses are performed. There will be a single key to the coded data kept on a password protected computer. Computer files containing names, addresses or other identifiers will be limited to authorized personnel at the site who have access to the computer data base using a password protected program. All investigators, professional medical staff, and technicians are aware of the confidentiality involved with the proper conduct of such a study. Consistent with the conduct of human research studies, the data will not be available or divulged to anyone outside of the experimental research team. The results from the study may be published, but will have no identifiers.

Radiation Treatment. Possible Side Effects of Radiosurgery (Radiation)

	COMMON, SOME MAY BE SERIOUS
	In 100 people receiving radiation therapy, 20 to 100 may have:
•	If a head frame is used, temporary (short-term) pain from the
	head frame placement

OCCASIONAL, SOME MAY BE SERIOUS

In 100 people receiving radiation therapy, 4 to 20 may have:

- Headache
- Tiredness
- If a head frame is used, bleeding and/or infection around the head frame pin sites

RARE, SOME MAY BE SERIOUS

In 100 people receiving radiation therapy, 3 or fewer may have:

- Nausea
- Reddening of the skin
- Localized hair loss which may be permanent

RARE, AND SERIOUS				
	In 100 people receiving radiation therapy, 3 or fewer may have:			
•	Decreased brain function such as motor function (coordination/movement)			
•	Swelling of the brain in the treated area which may require steroids			
•	Severe local damage to or death of normal brain tissue, which may require surgery to remove			
•	Seizure			

Ketogenic Diet. There are no significant risks associated with consuming a well-formulated ketogenic diet. For patients using medication to control blood sugar and blood pressure, there is a need to reduce these medications rather quickly at the onset of the diet to prevent low blood sugar and hypotension. In this study, we will exclude those patients who have type-2 diabetes using insulin. In our prior research we have assessed thousands of metabolic panels in patients assigned to ketogenic diets. Abnormal responses are rare, but it is expected that there will be modest changes in some metabolic parameters. These markers are expected to remain within normal limits and not pose a serious concern. For example, uric acid levels often increase during the first few weeks of a ketogenic diet and then return to or below baseline after 1-2 months. This transient increase does not exacerbate gout or have other untoward effects, since the elevation is due to competition with ketones for renal excretion, in contrast to increased intracellular synthesis of uric acid. Nutritional ketosis is associated with natriuresis (increased loss of sodium in the urine) and fluid loss. If the extra sodium excreted is not compensated for in the diet, the subsequent contracted plasma volume can manifest in side effects and adrenal stress including a hormonal response that disrupts body mineral status. Our diets contain adequate sodium and potassium to ensure mineral nutriture. The diet intervention may be challenging for participants since it will require them to limit foods, they are accustomed to eating. Participants will be made aware of the general dietary requirements including lists of foods they will need to restrict (as well as foods that will be permitted) during the informational session, so they can make an educated decision to participate.

Body Composition. The DXA scan has a risk that is negligible, as the skin entrance dose of radiation due to the application of the exam is very small. In a whole-body scan, which is the mode used in this project, the skin entrance dose of radiation per scan is ~ 0.04 millirem. On average in the US a person receives ~ 0.85 millirem per day of background radiation. For another comparison, a chest X-ray delivers $\sim 10-20$ millirems per scan. Thus, the level of radiation exposure is extremely low. Since we don't know what effect the radiation could have on an unborn baby, we will perform a urine pregnancy test before the scan for all women of child bearing age in the study.

Blood Draws. Blood draws by venipuncture may cause discomfort at the puncture site and the development of a slight bruise. Participants may also experience lightheadedness or fainting during the blood draw and there is a slight risk of infection. All blood draws will be taken by trained phlebotomists. The total blood volume at each testing session will be less than 50 mL, which translates into less than 200 mL over 6 months.

Ketone Testing. Ketone testing will be done daily by finger stick using a small 26G lancet. There is slight transient discomfort associated with this procedure.

This is a diet intervention study and thus no risk for toxicity exists beyond that normally present during typical treatment. Nevertheless, we will record type of modification and toxicity management

in detail for each patient.

The severity of adverse reactions is categorized as grade 1 to grade 5 in increasing severity. General descriptors for the toxicity grades range from none to fatal:

Grade 1 – Mild (The adverse reaction does not interfere in a significant manner with the subject's normal functioning level. It may be an annoyance.)

Grade 2 – Moderate (The adverse reaction produces some impairment of functioning but is not hazardous to health. It is uncomfortable and/or an embarrassment)

Grade 3 – Severe (The adverse reaction produces significant impairment of functioning or incapacitation and is a definite hazard to the subject's health)

Grade 4 – Adverse reactions that include or lead to either a) a life-threatening event, though acute and without permanent effect, b) prolonged inability to resume usual life pattern, or c) impairment of ability to adequately deal with future medical problems

Grade 5 – Death related to AE

Toxicity will be monitored during study visits and telephone calls using the National Cancer Institute Common Terminology Criteria for Adverse Events v4.0 (CTCAE) of the National Cancer Institute will be used (http://evs.nci.nih.gov/ftp1/CTCAE/CTCAE_4.02_2998-09-15_QuickReference_5x7.pdf). Grade 3, 4 and 5 toxicities will be reported as adverse events. Patients with Grade 3-4 adverse reactions that are related to the diet will be removed from the study.

The attribution of each toxicity will be ascertained by treating physician to both standard therapy as well as to diet intervention during the study. Treating physicians will manage suspected toxicity for dose holds and dose modifications as part of standard of care according to package insert recommendations.

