5.0 OBJECTIVES

We propose to conduct a highly controlled feeding study for 16 weeks to examine the effects of an individualized ketogenic or American Institute of Cancer Research (AICR) dietary approach on tumor response to targeted radiation therapy, as well the neural preservation in non-targeted areas of the brain. Our specific aims are as follows:

Primary objective: Assess the feasibility of maintaining a ketogenic versus AICR diet in patients with brain metastasis selected for radiosurgery. Endpoints:

- Circulating glucose (primary endpoint)
- Circulating ketones (primary endpoint)
- Retention
- Side-effects

Secondary objective: Assess the preliminary efficacy of the ketogenic versus AICR diet on tumor response to targeted radiation therapy. Endpoints:

• RECIST v. 1.1 will be utilized to evaluate responses to therapy

Exploratory objective: Assess the preliminary effects of the ketogenic versus AIRC diet on cognitive function and quality of life in BM individuals undergoing radiation therapy.

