6.0 STUDY DESIGN

This pilot study will be a single center, randomized controlled study of 24 participants with diagnosed BM (various primary disease sites) comparing the effect of a ketogenic (n=12) and AICR (n=12) diet. Randomization will be balanced by blocks of random sizes but no stratification due to the small sample size. Both groups will undergo a 16-week diet intervention. In an effort to maintain a patient centric focus and monitor changes in quality of life (QOL) all patients will complete psychosocial and behavioral inventories. These inventories aim to capture a holistic view on the proposed nutritional intervention during treatment. Primary outcomes will be determined at baseline, 8 weeks, and 16 weeks (see section 13 - Study Calendar) while patient-centric outcomes will be assessed every four weeks.

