12.0 ADVERSE EVENT REPORTING

12.1 Definition

Adverse event: Any unfavorable and unintended sign (including abnormal laboratory finding), symptom, or disease temporally associated with the use of a medical treatment or procedure, regardless of whether it is considered related to the medical treatment or procedure; also an "unanticipated problem" of any nature (e.g., psychological or social harm) (designated as unrelated, definitely related, probably related, or possibly related; see below)

Serious adverse event: Any adverse event that is fatal or life threatening, is permanently disabling, requires inpatient hospitalization or prolongs hospitalization, or results in a congenital anomaly or birth defect

Life-threatening event: Any adverse event in which the subject is at immediate risk of death from the reaction as it occurs; does not include a reaction that, if it were to occur in a more serious form, might cause death

Unexpected event: Any adverse event that is not identified in nature, severity, or frequency in the investigator brochure, study protocol, consent form, or IND application; or the event was more serious than anticipated

Association:

Definitely Related: An adverse event that has a timely relationship to the administration of the investigational drug/study procedure and follows a known pattern of response which no alternative cause is present

Probably Related: An adverse event that has a timely relationship to the administration the investigational drug/study procedure and follows a known pattern of response, but which a potential alternative cause may be present

Possibly Related: An adverse event that has a timely relationship to the administration the investigational drug/study procedure, follows no known pattern of response, potential alternative cause does not exist

Unrelated: An adverse event for which there is evidence that it is definitely a related cause other than the investigational drug/agent; in general, no timely relationship administration of the drug/procedure exists, or if so, the event does not follow a pattern response and an alternative cause is present

The Common Terminology Criteria for Adverse Events v4.0 (CTCAE) of the National Cancer Institute will be used. The severity of adverse reactions is categorized as grade 1 to grade 5 in increasing severity. Grade 3, 4 and 5 toxicities will be reported as adverse events. General descriptors for the toxicity grades range from mild to fatal:

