15 CRITERIA FOR REMOVAL OF PATIENTS FROM PROTOCOL THERAPY

Study patients may voluntarily withdraw at any time from the protocol. If a treating physician elects to remove a patient from the study, the Principal Investigator must be notified of withdrawal from the protocol. The reasons for discontinuation of the study must be documented in the patient record and data collection forms. Patients experiencing irreversible Grade 3-4 toxicity that is clearly related to the study treatment will be removed from the protocol. Patients with documented progression of disease will be removed from the protocol.

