17.0 STATISTICAL ANALYSES

Analysis Plan

Unless otherwise specified, all analyses will proceed on an intent-to-treat basis, and hypothesis tests will be two-sided and at the 5% significance level.

The primary objective is to assess the feasibility of maintaining a ketogenic versus AICR diet in patients with brain metastasis selected for radiosurgery. The primary measurements are blood levels of glucose and ketones. Measurements will be taken at baseline, 8 weeks, and 16 weeks. These biomarker outcomes will be analyzed using mixed effects linear regression with fixed effects for timepoint, diet group, their interaction, BMI, and sex. We will use subject-level intercept random effects to account for correlation between repeated measurements within subjects. The primary targets of inference are the treatment effects at each (post-baseline) timepoint. To test the two primary measurements at the two post-baseline timepoints, we will use a 4-way Bonferroni-Holm correction to account for multiplicity. Retention at week 8 and 16, as well as side effects, will be summarized and compared between diet groups.

To assess the preliminary efficacy of ketogenic versus AICR diet on tumor response to targeted radiation therapy, we will use a Chi-squared test for the association between treatment group and partial-or-complete response according to RECIST v1.1.

For the exploratory objective assessing the preliminary effects of the ketogenic versus AICR diet on quality of life in BM individuals undergoing radiation therapy, we will use the same linear mixed effects model as for the primary objective, but with the following quality-of-life endpoints as outcomes: Hearth Hope Index, SF-36, FACT-B, Brief Pain Inventory, and Brief Fatigue Inventory. Tests will be performed without multiplicity correction.

The mixed models used for the primary analyses are applicable to unbalanced data due to chance imbalances, missing data, or drop-out. We will assess the possible impact of non-random missingness using sensitivity analyses.

Power Analysis

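### Sections 11 and 15 set different toxicity criteria for mandatory removal, and the protocol does not say which one governs

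*Protocol*

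**What the plan says.** The protocol states a toxicity rule for removal in two places.

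- Section 11 (Potential Risks and Management): "Patients with Grade 3-4 adverse reactions that are related to the diet will be removed from the study".
- Section 15 (Criteria for Removal of Patients from Protocol Therapy): "Patients experiencing irreversible Grade 3-4 toxicity that is clearly related to the study treatment will be removed from the protocol".

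Section 15 also allows voluntary withdrawal and removal at a physician's choice: "If a treating physician elects to remove a patient from the study, the Principal Investigator must be notified of withdrawal from the protocol". Neither section refers to the other.

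Section 12.1 grades relatedness in four levels ("designated as unrelated, definitely related, probably related, or possibly related; see below"), but neither removal rule says which of these levels it means.

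Section 5.0 gives the aim as follows: "Primary objective: Assess the feasibility of maintaining a ketogenic versus AICR diet in patients with brain metastasis selected for radiosurgery". Four endpoints stand under it. Glucose and ketones are marked as primary endpoints; retention and side effects are listed without that mark. Section 17.0 says how the latter two are used: "Retention at week 8 and 16, as well as side effects, will be summarized and compared between diet groups".

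**The concern.** Both sentences are mandatory, but their conditions differ. Section 11 asks only that a Grade 3-4 reaction be related to the diet. Section 15 adds that it be irreversible and that the relation be clear, and it names the study treatment as the cause.

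The first consequence is for safety conduct: two members of staff, each following the protocol, could handle the same event differently. The second is for the feasibility result. Removal feeds into retention and can change how long a patient is exposed to the diet and observed for side effects. Both are compared between arms, so part of an observed difference could come from which section was followed.

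**Working it through.** **Step 1. The two rules side by side.**

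| Element | Section 11 | Section 15 |
|---|---|---|
| Grade | 3-4 | 3-4 |
| Reversibility | no condition | must be irreversible |
| Attribution | related | clearly related |
| Cause | the diet | the study treatment (not defined relative to the diet) |
| Force | mandatory | mandatory |

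**Step 2. Test cases, all Grade 3-4 and attributed to the diet.**

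- Irreversible, definitely related: meets section 11. It meets section 15 if the study treatment includes the diet.
- Reversible, definitely related: meets section 11, does not meet section 15.
- Irreversible, only possibly or probably related: meets section 11 if those levels count as related; it is doubtful whether it meets section 15.
- Acute life-threatening event that leaves no lasting effect, which the protocol's Grade 4 definition (sections 11 and 12.1) expressly includes: meets section 11 if related to the diet, and appears to fall outside section 15.

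So the mismatch is not confined to Grade 3.

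**Step 3. Size for retention.** Section 6.0 gives the allocation: "comparing the effect of a ketogenic (n=12) and AICR (n=12) diet". If a removed patient is counted as not retained, one patient whose removal depends on the section read is 1/12 = 8.3 percentage points of that arm's retention. The protocol gives no expected number of such events, so the number k is an assumption, shown here from 1 to 4 in the ketogenic arm with other losses set aside. Retention under section 11 is (12 − k)/12; under section 15 alone it would be 100%.

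**Step 4. Size for power.** Inputs from the Power Analysis in section 17.0: 12 completers per arm; significance level 0.0125, two-sided; detectable differences 2.3 mg/dL (glucose) and 0.34 mmol (ketones); standard deviations of change 1.077 mg/dL and 0.16 mmol. Power comes from the noncentral t distribution with df = n1 + n2 − 2 and noncentrality d / (SD × √(1/n1 + 1/n2)).

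The plan's own figure first, with n1 = n2 = 12 and df = 22:

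- Glucose: 2.3 / (1.077 × √(1/12 + 1/12)) = 5.23; power 0.9905.
- Ketones: 0.34 / (0.16 × √(1/12 + 1/12)) = 5.21; power 0.9899.

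The stated 99% is reproduced. Now suppose that k ketogenic-arm patients are removed and also give no outcome data, so n1 = 12 − k:

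| k | Retention, section 11 | Retention, section 15 | Power, glucose | Power, ketones |
|---|---|---|---|---|
| 1 | 91.7% | 100% | 98.7% | 98.6% |
| 2 | 83.3% | 100% | 98.1% | 98.0% |
| 3 | 75.0% | 100% | 97.3% | 97.2% |
| 4 | 66.7% | 100% | 96.1% | 95.9% |

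On the protocol's own inputs, the effect falls on retention and hardly on power.

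**The case against.** The strongest reply is that the two sentences can both be obeyed. Each says when a patient is to be removed; neither says when a patient must stay. A reader might infer that section 15 obliges staff to keep a patient whose event is reversible. The text does not support that: section 15 contains no such duty and allows a physician to remove a patient by choice. What remains is that, if both rules apply together, the conditions of irreversibility and clear attribution do no work for diet-related events. Section 15 is also where a reader would look for the complete list of criteria.

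A second reply is that the rules address different causes, since section 7 covers radiosurgery as well as diet and section 11 has toxicity attributed separately to standard therapy and to diet. That may be the intention. But the study treatment is not defined, and the randomized intervention is the diet, so the rules overlap on diet-related events unless the protocol says otherwise.

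Two further inferences should not be drawn. Section 11 speaks of leaving the study and section 15 of leaving the protocol, but the sentence on physician-elected removal in section 15 uses both words for the same act, so this is not a separate conflict. Nor can it be said that a removed patient loses the week 8 and week 16 measurements: the documents do not say that removal ends data collection. Section 17.0 specifies intent-to-treat analysis, mixed models that accommodate missing data, and sensitivity analyses for non-random missingness. Section 13 treats anyone who took the intervention for any period as evaluable.

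Finally, 8.3 points is what any single loss costs in an arm of 12, and the protocol expects abnormal metabolic responses to be rare. Both points stand and limit the expected size of the problem. They do not settle which rule applies when an event occurs.

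**Conclusion.** The mismatch is real on reversibility and on strength of attribution, and it is left open on cause because the study treatment is not defined relative to the diet. A diet-related Grade 3-4 event that is reversible or less than clearly attributed requires removal under section 11 and does not meet the criterion in section 15; no text gives precedence.

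The main weight lies on consistent safety conduct. Statistically, each affected patient counts for 8.3 percentage points of an arm's retention, on the assumption that a removed patient is counted as not retained. The side-effect comparison can shift as well, by an amount that the documents do not allow to be calculated. Both are endpoints of the primary objective, though not tagged as primary endpoints. The stated 99% power is little affected, staying at about 96% or above with up to four ketogenic-arm patients giving no data. Any loss of later measurements depends on what removal ends, which is not stated. The point should be corrected, but it does not undermine the primary analysis of glucose and ketones.

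**What to change.** The investigators should reconcile the removal sentences in sections 11 and 15 into a single rule, stated in one place and cross-referenced from the other. The rule should say:

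- whether reversibility matters;
- which relatedness levels from section 12.1 trigger removal;
- whether the cause in question is the diet, the study treatment or either, with the study treatment defined;
- whether removal ends the diet, follow-up or both, so that retention and the intent-to-treat data are counted in the same way in both arms.

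Which clinical rule is right is for the investigators to decide; this review does not propose one. The cost is wording in a protocol amendment, with the IRB approval that section 16.1 requires for every amendment. Sample size and planned analyses do not change.
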